6.1 Study Visits

6.1.1 Screening Period

Study participants entering this study within 2 weeks of completing the EOT visit of OV101-19-001 do not need to have a screening period; the screening activities can be verified or conducted at the baseline (Day 1) visit. All other study participants will be screened for participation in the study up to 30 days before Baseline (Day 1), when the first dose will be administered. Study participants who meet all entry criteria can have their baseline clinic visit at any time during the screening period.

Written informed consent (from the study participant's LAR/caregiver) and assent (from the study participant) will be obtained before the study participant participates in any study procedure and begins the study screening procedures for eligibility. Assent will be obtained if the investigator believes that the study participant has the intellectual capacity to provide it, but assent may not be relevant based on the study participant's intellectual disability and/or age (Section 9.3).

Molecular confirmation of the diagnosis of AS was an inclusion criterion for OV101-15-001, OV101-16-001, and OV101-19-001. Blood tests for molecular confirmation of AS will not be performed unless the study participant is a sibling of a previous participant and does not have prior documented molecular confirmation.

During the screening period, the investigator will determine whether the LAR/caregiver and study participant are able to complete all questionnaires and assessments that require their contributions and will also assess their ability to comply with study procedures.

In preparation for participation in this trial, LAR/caregivers will be educated on the clinical safety data for OV101 obtained thus far and will be trained to report assessments and to identify, manage, and report any potential AEs.

The LAR/caregiver will be provided with a sleep diary for documenting the study participant's sleep and a seizure diary for documenting the study participant's seizures. The LAR/caregiver will record data in the sleep diary for at least 7 days before each clinic visit. A calendar reminder will also be provided for recording data in the sleep diary.

A study participant who does not meet the inclusion criteria or who meets an exclusion criterion will be considered a screen failure. Whether rescreening is acceptable will be discussed with the medical monitor. Rescreening will only be allowed once and only in cases where no safety risk is posed to the study participant (Section 4.2.3).

If a screening test result (laboratory or any other test) is considered uncertain or abnormal, the test may be repeated to confirm the result after approval from the medical monitor or designee.

6.1.2 Baseline Visit

For study participants entering this study within 2 weeks of completing the EOT visit of OV101-19-001, the EOT visit activities need not be repeated at the baseline visit. The EOT visit of OV101-19-001 can serve as the baseline visit for the present study. Screened study participants will return to the study site for the baseline (Day 1) visit, and the LAR/caregiver will bring the study participant's completed sleep and seizure diaries for review by study staff. Study staff will collect the sleep diary (for recording in the eCRF) and will review it for completeness. If quality issues are detected, study staff will again instruct the LAR/caregiver in the proper use of the sleep diary. A new sleep diary will be issued to the LAR/caregiver for use in the 7-day period preceding the Week 2 clinic visit. A calendar reminder will also be provided for the start of sleep diary assessments.

Before dispensing study drug, study site staff must confirm appropriate completion of the sleep and seizure diaries and fulfilment of all eligibility criteria (Section 4.1). Study participants who meet all eligibility criteria will receive study drug at Baseline as described in Section 5.2.

Screening and baseline assessments must be performed within a 30-day period. If the screening and baseline visits are separated by no more than 14 days, the following assessments do not need to be repeated at the baseline visit: medical history, clinical assessment, physical examination, clinical laboratory tests, and determination of concomitant medications.

6.1.3 Phone Visits for Dose Titration

Phone visits are scheduled to assess each study participant's tolerance for OV101 and to determine how to continue the dose titration. The investigator may initiate additional phone visits for managing dose titration or adjustment at his/her discretion. Phone visits for dose titration of all study participants will be scheduled for Days 6 and 11.

The LAR/caregivers will be queried about AEs, concomitant medications, and study participant suicidality (Table 6-1). Detailed instructions for the phone visits are presented in the investigators' phone visit study manual. Results of inquiries about AEs and changes in concomitant medications and assessment of suicidality must be documented and recorded in the eCRF.

6.1.4 Telehealth/Virtual Visits at Weeks 24, 48, 80, 112, and 144

Phone visits by a nurse, nurse practitioner, or similarly qualified person are scheduled during Weeks 24, 48, 80, 112, and 144 to conduct assessments as detailed in Table 6-1. Detailed instructions for the phone visits are presented in the investigators' virtual/ phone visit study manual. A home nurse visit will replace a virtual visit if the latter is not feasible.

6.1.5 Clinic Visits at Weeks 12, 36, 64, 96, and 128

Study participants will return to the study site for the Week 12, 36, 64, 96, and 128 visits. The LAR/caregiver will bring the study participant's completed sleep diary, seizure diary, medication diary, and study drug in original containers for review by study staff. Study staff will collect the sleep diary (for recording in the eCRF) and will review it for completeness. If quality issues are detected, study staff will again instruct the LAR/caregiver in the proper use of the sleep diary. New sleep and seizure diaries will be issued to the LAR/caregiver for use in the 7-day period preceding the next clinic visit. A calendar reminder will also be provided for the start of sleep diary assessments.

Review of the seizure diary will occur as described in Section 6.2.2.4.

Before dispensing study drug, study site staff must confirm appropriate completion of the sleep and seizure diaries and continued fulfilment of all eligibility criteria (Section 4.1). Study participants who continue to meet all eligibility criteria will receive study drug at Weeks 12, 36, 64, 96, and 128.

6.1.6 Week 160 or End-of-Treatment Clinic Visit

Study participants will return to the study site for the Week 160 visit. An EOT visit, with the same assessments as the Week 160 visit, should be scheduled for a study participant who discontinues study treatment before Week 160.

The LAR/caregiver will bring the study participant's completed sleep diary, seizure diary, medication diary, and study drug bottles/cards for review by study staff. Study staff will collect the sleep diary (for recording in the eCRF) and will review it for completeness.

6.1.7 End-of-Study Phone Visit

The EOS phone visit is scheduled to occur 2 weeks after the EOT visit to assess each study participant's response to discontinuation of treatment with OV101.

The LAR/caregivers will be queried about AEs, concomitant medications, and study participant suicidality (Table 6-1), and the investigator (or designee) will conduct the Clinical Global Impressions-Severity-Angelman syndrome (CGI-S-AS) and Clinical Global Impressions-Improvement-Angelman syndrome (CGI-I-AS) assessments. Detailed instructions for the phone visits are presented in the investigators' phone visit study manual. Results of inquiries about AEs and changes in concomitant medications and assessment of suicidality must be documented and recorded in the eCRF.

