3.1 Study Design

This will be an open-label, long-term safety study for evaluation of treatment with OV101 in approximately 170 study participants with AS who either have completed previous Ovid studies (OV101-15-001, OV101-16-001, or OV101-19-001) or are siblings (with AS) of study participants with AS who have completed previous Ovid studies of OV101. There will be no placebo treatment. The study will be conducted at approximately 20 sites (total) in the United States, Australia, Europe, and Israel. As this study will enroll study participants who may have completed previous studies for different periods of time before entering this study (as well as study participants with AS who have not been themselves enrolled in an Ovid study), study participants may be required to complete screening and baseline visits before receiving OV101 under this protocol.

The study will comprise a screening period of up to 30 days; a baseline visit on Day 1 for baseline assessments; it is recommended that first dose of study drug be taken at the site unless a patient is unable to attend a clinic visit in person (e.g. due to COVID-19 restrictions) in which case the first dose of study drug to be taken in the evening of Day 1 (at bedtime), and clinic visits for safety and efficacy assessments over a 3-year treatment period (Figure 3-1). After the baseline visit, the clinic visits will occur at Weeks 12, 36, 64, 96, 128, and 160 (end of treatment [EOT]). If a patient cannot attend an in-person visit, a home visit may be conducted by a trained mobile healthcare professional to perform study assessments e.g. vital signs, body system assessment, clinical lab draws, review/collection of study materials.

Telehealth/virtual visits will occur at Weeks 24, 48, 80, 112, and 144. A follow-up phone safety visit at the end of study (EOS) will occur approximately 14 days after the last dose of study drug (EOT) to assess safety and tolerability associated with discontinuation of treatment. A home nurse visit will replace a virtual visit if the latter is not feasible. A study participant will be considered to have completed the study after completing the EOS phone visit. The schedule of activities for this study is fully presented in Table 6-1.

Figure 3-1 Study Design Schematic

*All study participants will be titrated in accordance with the titration schedule.

*Neptune study participants EOT visit may serve as a baseline visit for ELARA.

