6.2.1 Adverse Events

6.2.1.1 Definitions of Adverse Events

The investigator is responsible for reporting all AEs that are observed or reported during the study, regardless of their relationship to study drug or severity. Each study participant's LAR/caregiver will be instructed to contact the study center if the study participant experiences any AEs, including whether there was any change in the study drug administration (e.g., dose withheld, dose reduced, or dose missed).

An AE is defined as any untoward medical occurrence in a study participant enrolled into this study regardless of its causal relationship to study drug. Each study participant's LAR/caregiver will be instructed to contact the investigator at any time after enrollment if any new or worsening symptoms develop.

Treatment-emergent AEs (TEAEs) are defined as AEs that start or increase in severity after the first dose of study drug in this open-label study. All AEs occurring after the study participant receives the first dose of study drug must be reported to Ovid or its designee via the eCRF.

Anticipated day-to-day fluctuations of preexisting disease(s), condition(s), or behavior(s) present or detected at the start of the study that do not worsen are not AEs. Lack of drug effect is not an AE. Social and/or convenience situations and/or admissions to the hospital, where an untoward medical occurrence did not occur, are not AEs.

Cases of pregnancy that occur during maternal or paternal exposures to study drug are to be reported. Data on fetal outcome and breastfeeding are collected for regulatory reporting and drug safety evaluation.

Study staff will record the occurrence and nature of each study participant's preexisting conditions (e.g., prior to enrollment in ELARA), including clinically significant signs and symptoms of the disease under treatment in the study (e.g., seizures, motor dysfunction, sleep disruption, anxiety), as part of the medical history.

As seizures are often a baseline condition in study participants with AS, seizures should be reported as an AE in any of the following circumstances:

- There is a clear increase in the frequency of seizures compared to the study participant's baseline.
- There is an emergence of a new seizure type.
- The study participant experiences status epilepticus.
- The investigator believes the seizure should be captured as an AE (in which case the investigator should document their reasoning).

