7.7.1 Analysis of Primary Endpoints - Safety

All safety analyses will be performed on the SS.

All AEs will be coded using latest version of MedDRA and will be classified by MedDRA system organ class (SOC) and preferred term (PT).

The number and percentage of study participants who experience at least 1 TEAE as well as the 95% exact CI for the incidence of TEAEs overall and within each specific SOC and PT will be presented.

Treatment emergent adverse event is defined as newly or worsening AEs start from the first dose of study medication till 30 days after the last dose of study medication.

Treatment-related AEs will be identified as those that are at least possibly related to study drug based on the investigator's assessment. The number and percentage of study participants with treatment-related AEs, SAEs, TEAEs leading to study discontinuation, and TEAEs leading to death will also be summarized by SOC and PT.

For each SOC and each PT, a study participant will be counted only once for study participant-incidence tabulations. For summaries by severity or relationship, for a given study participant, the highest severity and relationship for a specific PT will be considered.

Descriptive statistics for the observed values and changes from baseline to each post baseline visit with respect to clinical laboratory and vital sign measurements will be summarized. Clinically significant laboratory values may be tabulated.

Shift tables for laboratory parameters will be presented. For each continuous laboratory parameter, results will be categorized as low, normal, and high based on the laboratory normal ranges. Frequencies and percentages will be presented for the shifts in these categories from baseline to each posttreatment assessment timepoint.

Suicidality assessed by ABC-I will be summarized descriptively at baseline and all post baseline study visits. Change from baseline to all post baseline study visits also will be summarized descriptively.

Abnormal findings in physical examinations will be listed.

The 28-day seizure frequencies as captured in the seizure diary will be calculated for baseline and post baseline study periods for all seizure types and for subtypes of drop and nondrop. Percent change in 28-day seizure frequency from baseline to all post baseline study visits will also be summarized descriptively for all seizure types and for subtypes of drop and nondrop.

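### Section 7.7.1 plans no adverse event summary that separates onset after the last dose from onset on drug, so the AE incidence tables cannot show the response to discontinuation that the EOS contact is meant to assess

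*Combined protocol and SAP*

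**What the plan says.** **Purpose of the EOS contact.** Section 3.1 places a phone visit about 14 days after the last dose "to assess safety and tolerability associated with discontinuation of treatment". Section 6.1.7 says it is there to assess each participant's "response to discontinuation of treatment with OV101".

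**Planned AE analysis.** Section 7.7.1 defines treatment-emergent events (TEAEs) as "newly or worsening AEs start from the first dose of study medication till 30 days after the last dose of study medication". Its counting rule is "For each SOC and each PT, a study participant will be counted only once for study participant-incidence tabulations". For severity and relationship summaries, "the highest severity and relationship for a specific PT will be considered". No AE summary in Section 7.7.1 is broken down by onset relative to the last dose.

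**A second definition.** Section 6.2.1.1 describes TEAEs as "AEs that start or increase in severity after the first dose of study drug in this open-label study", which has no end point.

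**What is collected.** AE onset time is an eCRF item (Section 6.2.1.4), and the medication diary confirms dosing dates (Section 5.6). AEs are collected to 30 days after the last dose (Section 6.2.1.3). Table 6-1 marks ABC-I at EOS, and Section 7.7.1 summarises it by visit and as change from baseline. Section 7.7 puts all collected data in by-participant listings and leaves detailed methodology to a separate SAP.

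**The concern.** The protocol sets up a contact to learn what happens when OV101 is stopped, but the AE tables that would report it have no place for the answer. A participant whose first event of a given type starts off drug is tabulated exactly like one whose event started on drug. A participant who already had that term on drug cannot be counted again when it returns.

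AEs matter particularly here because most other measures stop at end of treatment (EOT). The seizure diary runs only through EOT (Section 6.2.2.4), sleep diaries are collected only through EOT (Section 6.8.1.2), and Table 6-1 shows no laboratory tests, vital signs or CSHQ at EOS. For a 160-week completer, worse seizures or sleep after stopping would be captured mainly as an AE. At stake is whether the study report can describe the safety of stopping a drug taken for about three years.

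**Working it through.** The plan states no figure on this point, and Section 7.4 says the sample size of about 170 is not power-based, so there is no planned number to reproduce. The check has two parts.

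**1. What the rules do to an off-drug event**

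| Event starting after the last dose | Effect on the Section 7.7.1 tables |
|---|---|
| First occurrence of the PT in that participant | Adds 1 to TEAE incidence, not distinguishable from on-drug onset |
| Recurrence, non-serious, severity the same or lower (and judged no more related) | None |
| Recurrence of higher severity | Incidence unchanged; participant moves up in the severity summary, with nothing to show it arose off drug |
| Recurrence that is serious when the earlier event was not | TEAE incidence unchanged; enters the SAE table, again without timing |

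For a completer, treatment lasts 160 × 7 = 1120 days. The off-drug part of the window is 30 of 1150 days, or 2.6%.

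**2. Illustration of size (all incidences are assumptions)**

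Inputs: N = 170 (Section 7.4); 1120 days on drug and EOS on day 1134 (Table 6-1); 30 days off drug (Section 7.7.1). Assumed: p1 = incidence of one PT on drug, p2 = incidence in the 30 days after stopping, constant hazard on drug, and all 170 complete treatment and are followed off drug.

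- Hazard ratio, off drug to on drug = −ln(1 − p2) ÷ [−ln(1 − p1) × 30/1120]
- Pooled incidence = 1 − (1 − p1)(1 − p2) if independent, or p1 if every off-drug case is a prior case

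*p1 = 30%, p2 = 10%.* The on-drug hazard per 30 days is 0.3567 × 30/1120 = 0.00955, a 30-day risk of 0.95%. Off drug it is 0.1054. The ratio is 0.1054/0.00955 = 11.0. On-drug cases number 51 and off-drug cases 17. If independent, 17 × 0.7 = 11.9 are added and 5.1 are absorbed, so the pooled figure is 62.9/170 = 37.0%. If all 17 are prior cases, it is 51/170 = 30.0%.

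*p1 = 10%, p2 = 5%.* The ratio is 0.0513/(0.1054 × 30/1120) = 18.2. The pooled figure is 14.5% if independent and 10.0% if all are prior cases.

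*p1 = 30%, p2 = 5%, independent.* The pooled figure is 33.5% (57/170; exact 95% CI 26.5 to 41.2), against 30.0% (51/170; 23.2 to 37.5) with no off-drug events. The intervals overlap almost entirely. A separate off-drug table would show 8.5 cases against 170 × 0.95% = 1.6 expected at the on-drug rate.

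**Why the split needs person-time.** In the first case, bare percentages by period would read 30% on drug and 10% off drug, which suggests fewer events after stopping. Rates per 100 participants per 30 days would read 0.96 and 10.5, which shows the 11-fold difference.

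**The case against.** The strongest case on the other side has five parts.

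- **Individual off-drug events are not lost.** This stands. Onset times and by-participant listings let a reader find each one. A reader might infer that the response to discontinuation cannot be seen at all, and the documents do not support that. But a listing has no denominator and no rate.
- **Other EOS data exist.** ABC-I at EOS is a planned by-visit summary, but as change from baseline rather than from EOT. Section 6.1.7 also calls for CGI-S-AS and CGI-I-AS at EOS, while their rows in Table 6-1 carry no EOS mark; the two must be reconciled. Neither replaces an AE summary.
- **The 30-day window is not an error.** This stands. A reader might infer that off-drug events wrongly inflate the primary safety result. But the primary objective (Section 2.1) is not limited to dosing days, the window matches AE collection in Section 6.2.1.3, and Section 7.7.1 does not label these events as on-drug. Nor do Sections 2.1 to 2.3 or 7.1 name discontinuation as an objective or endpoint. The split is an addition, not the correction of a wrong estimate.
- **The separate SAP may already have a split.** Possible; it is not among the documents. The point is therefore about Section 7.7.1, which fixes the window and the counting rule and, unlike Sections 7.6 and 7.7.3 on their topics, leaves nothing on discontinuation expressly to the SAP.
- **The magnitudes are assumed.** True. They show how the table behaves, not what OV101 does.

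**Conclusion.** The point holds as a gap in the AE summaries. Followed as written, the incidence tables in Section 7.7.1 cannot distinguish events that start after the last dose from those that start on drug, so they cannot serve the purpose that Sections 3.1 and 6.1.7 give the EOS contact. Listings, the by-visit ABC-I summary, and any shift in the severity or SAE tables give only partial information.

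That conclusion follows from the text and needs no numerical assumption. The size does: the 11.0-fold and 18.2-fold hazards, and the pooled figures of 30.0% to 37.0% and 10.0% to 14.5%, depend on assumed incidences, a constant on-drug hazard, and all 170 participants completing and being followed off drug. The last is optimistic, since the Synopsis lets participation end when the drug becomes commercially available. The change is worth making because it is cheap and uses data already collected.

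**What to change.** In Section 7.7.1 or the SAP:

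1. Keep the overall TEAE table. Add a descriptive table split by onset: (a) first dose to last dose, and (b) after the last dose to day 30.
2. Count a participant once per SOC/PT within each period, so that recurrence or worsening off drug counts in (b).
3. Give n, %, person-time and exposure-adjusted rates for each period. The denominator for (b) is participants who stopped drug and had post-dose AE follow-up.
4. Show (b) separately for 160-week completers and early stoppers, because their follow-up differs. Completers have one scheduled call at about day 14. Under Section 4.2, early stoppers have an EOT visit within 2 weeks of the last dose and an EOS visit within 2 weeks of that, so up to day 28.
5. Name this table as the analysis for the purpose stated in Sections 3.1 and 6.1.7.
6. Align the open-ended TEAE definition in Section 6.2.1.1 with Section 7.7.1.

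**Cost.** A few sentences and one more table set, with no new data collection. Counts in (b) will be small and intervals wide: even 17 of 170 gives an exact 95% CI of 5.9% to 15.5%. One limit remains. Section 6.2.1.7 does not require onset dates for each episode of an intermittent AE, so recurrences recorded that way may not reach (b); a footnote should say so.
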